10.3 Data used for meta-analysis

The protocol specifies that a meta-analysis should be included in the final report planned for December 2023. However, it is important to already now to investigate similarities and differences in the databases to be able to suggest the correct analysis to be done and not comparing different data from the three countries. The statistical methods will also by specified in this SAP. The calculations will be made by the Swedish statistician, e.g. no calculations are needed by BIPS or Statistics Denmark as shown in Table 6.

Objective	Denmark	Germany	Sweden	Meta- analysis
Primary objective, rate of low Na by diagnose code	Recorded from hospitals	Recorded from practitioners and specialists and hospitals*)	Recorded from hospitals	Maybe
Sec. Objective 1, descriptive statistics	Data	Data	Data	ОК
Sec. Objective 2, low Na treated at ICU	No data	No Data	Data from a specialized ICU register	Not possible
Sec. Objective 3, low lab. values of Na	Clinical database	No Data	No Data	Not possible
Sec. Objective 4, All-cause mortality	Data	Data (no reason for death)	Data	ОК
Sec. Objective 5a, MACE	Recorded from hospitals	Recorded from practitioners and specialists and hospitals*)	Recorded from hospitals	Maybe
Sec. Objective 5b, VTE	Recorded from hospitals	Recorded from practitioners and specialists and hospitals*)	Recorded from hospitals	Maybe
Sec. Objective 6, CHF	Recorded from hospitals	Recorded from practitioners and specialists and hospitals*)	Recorded from hospitals	Maybe
Sec. Objective 7, Comparing	Repeat primary analysis + sec. 2, 3, 4, 5a, 5b, 6.	Repeat primary analysis + sec. 2, 3, 4, 5a, 5b, 6.	Repeat primary analysis + sec. 2, 3, 4, 5a, 5b, 6.	Look at the other rows

T 11 5 0° 1 1	1.00	1 / /1			• 11 2	, ·
Table 5. Similarities and	differences	between th	he outcome	measures	in the 3	countries

Nocdurna ® vs LUTS Sec. Objective 8, treatment withdrawal	No Data	No Data	Data from drug registry	Not possible
Sec. Objective 9, treatment on label	Repeat primary analysis + sec. 3, 4, 5a, 5b, 6.	Repeat primary analysis + sec. 4, 5a, 5b, 6.	Repeat primary analysis + sec. 2, 4, 5a, 5b, 6.	Primary obj. + secondary 1-6

Abbreviations: ICU = Intensitive Care Unit, MACE = major cardiovascular events, VTE = major venous thromboembolic events, CHF = congestive heart failure. *) German data could be sub-divided and German data are discharge data (in-patient hospital care).

Comment to the table about meta-analysis.

It is obvious that there are major differences between the data collections in Germany on one side and Denmark/Sweden on the other side and also some difference between Denmark and Sweden. The Germany database also contains information from primary care and specialists, while the registries in Denmark/Sweden only contains information from hospitals, both in- and out-patient care. This issue concerns the primary objective, and secondary objective 5a, 5b, 6, 7 and 8. The effect will make the rates of the events higher in Germany, since events in primary care also are counted. However, the difference in effect between Nocdurna ® and LUTS could be expected to be more similar than the rate of events since there should be a similar increase in both groups when counting events in primary care. Also Danish and Swedish registries contain cause of death information (ICD 10 codes) that could partly be covered by German registries if the patient is hospitalized before dying at the hospital. Nocdurna ®

The deterministically linkage used by BIPS might also give a larger variance than the person-id linked data from Denmark and Sweden. However, the effect difference should be the same.

In secondary objective 2, 3, and 8 the data is only coming from one country and a meta-analysis is not possible, while secondary objective 9 is repeating the previous analysis taking contraindications for Nocdurna ® into consideration.

10.4 Meta-analysis of incidence rates

The descriptive tables in secondary outcome 1 will for the numeric variables like age be recalculated to give overall number of patients, mean and standard deviation, while the categorical variables will be recalculated to give frequencies and percentage covering the total population in Denmark, Germany, and Sweden. The method for re-calculation is shown in Figure 3.

The incidence rates (not the incidence rates ratios between the outcomes) will be combined by calculating the weighted mean and a new standard deviation for the 95% CI around the combined mean. The new standard deviation will be calculated according to the formulae given below.

	Group 1 (e.g. males)	Group 2 (e.g. females)	Combined groups
Sample size	N ₁	N_2	N ₁ + N ₂
Mean	M ₁	M ₂	$\frac{N_{1}M_{1} + N_{2}M_{2}}{N_{1} + N_{2}}$
SD	SD ₁	SD_2	$\sqrt{\frac{\left(N_{1}-1\right) S D_{1}^{2}+\left(N_{2}-1\right) S D_{2}^{2}+\frac{N_{1} N_{2}}{N_{1}+N_{2}} \left(M_{1}^{2}+M_{2}^{2}-2 M_{1} M_{2}\right)}{N_{1}+N_{2}-1}}$

Figure 3. Formulae for combining groups.

From (Cochrane Handbook, 2011)

10.5 Meta-analysis of incidence rate ratios

The results for incidence rate ratios (calculated according to secondary objective 7) will undergo a meta-analysis and be combined between the countries according to this section and illustrated in the tables (Table 61 to Table 65) and the figures (Figure 21 to Figure 30). The outcomes included in the meta-analysis are the primary objective, and for the secondary objectives 4, 5a, 5b, and 6.

The approach used is published by (Senn et al., 2011)

First the heterogeneity will be calculated and a p-value for the test if there is any heterogeneity will be calculated.

The formula used is computes I-square for the Q test for odds ratios as

 $I^2 = \max (100\% x (Q - (k - 1))/Q; 0)$

Where k is the number of strata and Q is a Q test for homogeneity of odds. This is implemented in the PROC FREQ procedure in SAS.

For interpreting I², (Higgins et al., 2003) suggest

 $I^2 = 0$ %, no heterogeneity, $I^2 = 25$ %, low heterogeneity, $I^2 = 50$ %, moderate heterogeneity, $I^2 = 75$ %, high heterogeneity. We should expect low heterogeneity.

A plot similar to the forest plot will be created for each of the outcomes showing the overall rate as illustrated in figure Figure 21. A Galbraith plot gives the same information as the forest plot, but

Ferring Pharmaceuticals

with another focus, where countries deviating from the mean are more easily detected as seen in Figure 21.

A funnel plot will be made. In a funnel plot should all points be in a triangle around the center vertical line as in Figure 22. If the parts of the triangle is missing, there could be a bias in the distribution or a classical bias in not publishing studies with negative results.

The sensitivity plot, in Figure 22, show the difference between a fixed model and a random model. The y-value for low values on the horizontal axis gives the value of a fixed model. In this figure the bold curve is decreasing indicating that the random effect is lower in absolute difference between treatments than the fixed effect model. It should be expected that a random model will have larger confidence intervals.

An analysis of using a fixed effect or random effect model demands to have heterogeneity analyzed before judgements can be done and even with these analyses a precise determination can be difficult to make. If we are measuring the same effect a fixed effect model should be used. Otherwise, a random effect model should be used. If we were joining different studies from different countries with different outcome, we should use a random effect model. In this case we are measuring the same outcome, but in different countries and in different administrative systems and each country will have several administrative systems for the health care. Both random and fixed effect models analysis will be planned. An outcome table for the combined effect using both fixed effect models will be created showing the model type, the method, the estimated combined difference in treatment, the standard of the estimated combined difference together with upper and lower 95% CI of the estimated combined difference. An example is shown in Table 61.

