9.7.4 Meta-analyses

Assuming country-specific analyses have been completed, results for the analysis of primary and secondary outcomes that can be defined in all three countries can also be combined using a meta-analysis approach in order to achieve a more precise estimate of the observed measure of incidence rate and identify any potential country-specific patterns in the data. Incidence rates of the two different groups will be combined across the three databases. Because the current analysis will pool incidence proportions of sparse data, a logistic regression model with random intercept will be used to calculate the pooled the mean log odds, which will be back transformed to the probability scale to yield the median incidence proportion and 95% CI. A likelihood ratio test will be used to evaluate between-database heterogeneity. Database-specific incidence rates will be meta-analysed with a Poisson regression model with random intercept (25). The logarithm of the sum of patient-time at risk will be used as an offset variable to yield incidence rates per 1000 patient-years. Pooled incidence rates will be back-transformed from the logarithm scale to per 1000-patient-years unit.

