Observe that the *fixed logistic regression in italic* is the model suggested in the protocol. SOURCE DOCUMENT: meta_fixed.SAS GENERATED: 22:53:48 16JAN2021 DB version DEV: Simulated data, USERID: [name]

Figure 23. Meta-analysis. A Galbraith to the left and a forest plot to the right illustrating the difference between the countries for all-cause mortality.

Figure 24. Meta-analysis. A funnel plot to the left and a sensitivity plot to the right for incidence rate ratio of all-cause mortality.

Table 62. Meta-analysis of the combined effect using random and fixed model and 7 different methods for incidence rate ratio of all-cause mortality

Figure 25. Meta-analysis. A Galbraith to the left and a forest plot to the right illustrating the difference between the countries for major cardiovascular events.

Figure 26. Meta-analysis. A funnel plot to the left and a sensitivity plot to the right for incidence rate ratio major cardiovascular events.

Table 63. Meta-analysis of the combined effect using random and fixed model and 7 different methods for incidence rate ratio of major cardiovascular events

Figure 27. Meta-analysis. A Galbraith to the left and a forest plot to the right illustrating the difference between the countries for venous thromboembolic events.

Figure 28. Meta-analysis. A funnel plot to the left and a sensitivity plot to the right for incidence rate ratio of venous thromboembolic events.

Table 64. Meta-analysis of the combined effect using random and fixed model and 7 different methods for incidence rate ratio of venous thromboembolic events

Figure 29. Meta-analysis. A Galbraith to the left and a forest plot to the right illustrating the difference between the countries for congestive heart failure.

Figure 30. Meta-analysis. A funnel plot to the left and a sensitivity plot to the right for incidence rate ratio of congestive heart failure.

[figure not shown]
Table 65. Meta-analysis of the combined effect using random and fixed model and 7 different methods for incidence rate ratio of congestive heart failure

Analysis of several events for each patient (Optional)

Table 66. Optional. Incidence of symptomatic hyponatraemia in country, if there are more than 5% of the patients that are having more than 1 event

Repeat Table 9, but with a changed regression taking into account that there are several events for more than 5% of the patients. The SAS macro must be re-programmed.

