%NOCDURNA_MAC(baseline=baseline,eventdata=eventdata,compare=LUTS,out_table=out_tabl e,dir=dir,ttitle=ttitle);

The 'LUTS' value in the macro can be changed to e.g. 'Off label' when objective 9 is analysed. Please check that the columns are in the correct order in the output and not interchanged.

The SAS macro variable 'DIR' gives a reference to the directory where the RTF table is written, in the development case, the 'C:\temp' directory have been specified, but each site will have a designated directory for the output. Please observe that there is no ending '\' in this macro variable.

The last SAS macro variable 'TTITLE' gives both the headline of the table and the headline (title) of the figure generated inside the SAS macro. Please do not use any ',' inside the text string specified in the macro call.

That is all for the input datasets.

Calculations inside the macro.

The Poisson regression is performed and a calculation is used to calculate the yearly rates. This is the key analysis.

```
ods output ParameterEstimates=ParameterEstimates;
proc genmod data=to_poisson;
class class gender age_class;
model events = class age_class gender / dist=poisson link=log
offset=log_exposure scale=d type3;
store p1;
run;
ods output lsmeans=lsmeans;
proc plm source = p1;
  lsmeans class /ilink cl;
run;
quit;
```

The 'STORE P1' is generating data that can be used for post analysis calculations, in this case will the 'PROC PLM' use the 'P1' data collection.

After the yearly rate per 1000 patient years are calculated and merged together with the rest of the analysis and a 'PROC REPORT' is used for writing the output RTF file.

When the macro is run several time, be sure to exit the Word document between different runs of the SAS macro, if not the output file will be locked and SAS will not be able to write to the file.

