16.4 Meta-analysis

In the final report planned for December 2023 a meta-analysis will be done. The meta-analysis is planned for Q3 in 2023. Combining incidence rates and descriptive statistics are described in the text, but the programming meta-analysis of the incidence rate ratios is described below.

A suite of SAS macros have been developed to do this task sponsored by Novartis. These macros will be applied.

Table 69. Description of SAS macros used for meta-analysis

Macro name	Description	Link
Mabinary	To carry out various approaches to analyzing binary data including classic Mantel-Haenszel analysis but also, for example, the analysis of Normal-binomial mixtures using PROC NLMIXED	mabinary.sas
maforest	To produce so-called forest plots whereby individual trials are represented by horizontal lines joining lower and upper confidence limits with a plotting symbol for the estimate and a final line and symbol for the overall meta-analytic summary	maforest.sas
mafunnel	To produce funnel plots. These plot the treatment estimate on the horizontal axis and the reciprocal of the standard error of the treatment estimate on the vertical axis.	mafunnel.sas
magalbraith	To produce radial or Galbraith plots as described in Statistics in Medicine , 1988.7,889-894. These plot the Z-scores, that is to say the ratio of estimated treatment effect to standard error, against the reciprocal of the standard error, where the latter is calculated as for a fixed effects analysis.	magalbraith.sas
mainverse	To carry out classic fixed effects meta-analysis using inverse weighting by variances of treatment contrasts.	mainverse.sas
mapeterlee	To implement Lee's checks as described in Statistics in Medicine ,1999, 18 ,1973-1981.	mapeterlee.sas
maqq	To produce QQ plots of estimated treatment effects by trial.	maqq.sas
marandom	To carry out random effects analysis using the approach of DerSimonian and Laird (DSL), Controlled Clinical Trials , 1986,7,177- 188 and also using that of Hardy and Thompson(HT), Statistics in Medicine , 1996, 15 , 619-629.	marandom.sas
masensitivity	To examine the sensitivity of conclusions from random effects analysis to the magnitude of the random effects variance.	masensitivity.sas

There is also a sample program for showing the correct usage of the macros.

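### SAP 10.5 pools adjusted incidence rate ratios but defines heterogeneity, and three of its seven estimators, on binary-data odds methods

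*Protocol*

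**What the plan says.** - **What is pooled.** SAP 10.5: "The results for incidence rate ratios (calculated according to secondary objective 7) will undergo a meta-analysis". SAP 10.2.8 says objective 7 uses the same Poisson regression as the primary analysis, with the output changed to rate ratios. The model code in SAP 16.1 is "model events = class age_class gender / dist=poisson link=log" with "offset=log_exposure scale=d type3". It therefore carries treatment, age class, gender and log exposure. SAP 16.2 says the objective 7 macro, NOCDURNA_MAC7, takes the same input datasets.
- **How heterogeneity is measured.** SAP 10.5: "The formula used is computes I-square for the Q test for odds ratios as", followed by "Where k is the number of strata and Q is a Q test for homogeneity of odds". The section says this is implemented in PROC FREQ.
- **How the pooled value is estimated.** Table 61 is titled as pooling the IRR of symptomatic hyponatraemia, and Tables 62–65 repeat it for four other outcomes. It has seven rows. The fixed rows are Mantel-Haenszel, inverse variance and logistic regression. The random rows are DerSimonian-Laird, Hardy-Thompson Wald, Hardy-Thompson profile and normal-binomial mixture.
- **Which macros are used.** SAP 16.4 introduces the macro suite as the programming for the IRR meta-analysis. It describes mabinary as "To carry out various approaches to analyzing binary data including classic Mantel-Haenszel analysis", and places normal-binomial mixtures there too. It describes mainverse as weighting by variances of treatment contrasts, and marandom as the DerSimonian-Laird and Hardy-Thompson methods.
- **What the protocol is said to want.** The Table 61 footnote says the fixed logistic regression row "is the model suggested in the protocol".

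**The concern.** The section names one effect measure as its subject and prescribes tools for another. A homogeneity test on odds works on counts of patients with and without an event. It does not see how long each patient was observed, and the plan gives it no age or sex adjustment. The same holds for the three binary rows as they are described. Their output would stand under a title that calls it an IRR, next to rows that may really contain one.

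At stake is the pooled comparative safety result of a required post-authorisation study. SAP 10.3 argues that the contrast between NOCDURNA and LUTS should be more comparable across countries than the rates themselves, and SAP 10.5 expects low heterogeneity. If follow-up differs between cohorts, and differs by an amount that varies between countries, an odds-based I-squared can signal heterogeneity that the rate ratios do not have.

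**Working it through.** **1. Match the seven rows to the macro descriptions.**

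| Row in Table 61 | Type, as described | Can take an adjusted log IRR and SE? |
|---|---|---|
| Mantel-Haenszel | binary (mabinary) | no |
| Logistic regression | binary model | no |
| Normal-binomial mixture | binary (mabinary) | no |
| Inverse variance | generic contrast (mainverse) | yes |
| DerSimonian-Laird | generic (marandom) | yes |
| Hardy-Thompson Wald | generic (marandom) | yes |
| Hardy-Thompson profile | generic (marandom) | yes |

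Three of seven are binary. Four of seven could be fed correctly, but the SAP does not say what they receive. The only heterogeneity statistic is on odds.

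**2. Compare an odds ratio with an IRR.** With a constant rate r and follow-up t, the probability of an event is p = 1 − exp(−rt), so the odds are exp(rt) − 1. For small rt the odds are about rt, and

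OR ≈ IRR × (mean NOCDURNA time / mean LUTS time).

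The documents give no real rates or exposure lengths by cohort, so all values here are assumed. With a LUTS rate of 10 per 1000 person-years:

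| NOCDURNA / LUTS time (years) | True IRR | OR |
|---|---|---|
| 0.44 / 0.88 | 2.0 | (e^0.0088 − 1)/(e^0.0088 − 1) = 1.00 |
| 0.44 / 0.88 | 1.0 | (e^0.0044 − 1)/(e^0.0088 − 1) = 0.50 |
| 0.44 / 1.32 | 2.0 | (e^0.0088 − 1)/(e^0.0132 − 1) = 0.67 |
| 0.44 / 0.44 | 2.0 | (e^0.0088 − 1)/(e^0.0044 − 1) = 2.00 |

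Over a wider range (LUTS rates of 5 to 30 per 1000 person-years, LUTS follow-up 1 year, true IRR 1.0), follow-up ratios of 0.25, 0.5, 1 and 2 give odds ratios of about 0.25, 0.50, 1.00 and 2.01–2.03. The shift can go either way. With equal follow-up, replacing an IRR by an odds ratio makes almost no difference.

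**3. Effect on pooling and I-squared.** Assume a true IRR of 1.5 in every country, LUTS follow-up of 1 year, and these inputs:
- Follow-up ratios: 0.5 (Denmark), 1.0 (Germany), 0.75 (Sweden).
- LUTS rates: 10, 15 and 10 per 1000 person-years.
- NOCDURNA numbers from protocol 9.5.3: 1830, 2650 and 2610.
- LUTS numbers, reading SAP 3.1.2.1 as 300,000 in Denmark: 300,000, then × 2.3 = 690,000 (Germany) and × 1.7 = 510,000 (Sweden).

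Expected NOCDURNA events are 1830 × 0.010 × 1.5 × 0.5 = 13.7, 2650 × 0.015 × 1.5 × 1.0 = 59.6 and 2610 × 0.010 × 1.5 × 0.75 = 29.4. These drive the variances, so the exact LUTS numbers matter little.

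- Inverse-variance pooling of log IRR: 1.50, Q = 0, I² = 0%.
- Binary route: country odds ratios 0.75, 1.51 and 1.13; Mantel-Haenszel 1.22; Q = 5.84; I² = (5.84 − 2)/5.84 = 66%.

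**4. Effect of losing the age adjustment.** This does not depend on follow-up. Assume a four-fold rate in older patients, with 80% older in one cohort and 50% in the other. An adjusted IRR of 1.0 then becomes a crude ratio of (0.8 × 4 + 0.2)/(0.5 × 4 + 0.5) = 3.4/2.5 = 1.36.

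**5. The footnote against the protocol.** For incidence proportions, protocol 9.7.4 says "a logistic regression model with random intercept will be used". For incidence rates it specifies a random-intercept Poisson model with log patient-time as offset. Neither is a fixed logistic regression. SAP section 13 itself describes the protocol's meta-analysis as a random-effects model, and declares the addition of fixed-effect models but no move to odds-based methods.

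**The case against.** A reader might infer that the whole IRR meta-analysis discards person-time and the age-sex adjustment, so that the pooled result is confounded with follow-up length. The documents do not support that. SAP 10.5 states that the objective 7 IRRs are what is pooled, and four of the seven rows can take an adjusted log IRR with its standard error. The fault is an inconsistency plus silence about inputs.

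The follow-up shift is also conditional. No real exposure lengths by cohort are given, and the 0.44 and 0.88 years are assumptions. The Table 9 shell (simulated data) shows nearly equal means: 510.4/3512 = 0.145 years and 219.5/1488 = 0.148 years. Unequal follow-up is nevertheless plausible from the design. SAP 9.1.1 lets a LUTS exposure period continue across any LUTS preparation, while a NOCDURNA period counts NOCDURNA only. SAP 10.2.8 ends exposure at a switch between groups. SAP Amendment 1 reports that 63.5% (Sweden) and 65.7% (Denmark) of NOCDURNA patients also started LUTS drugs in the study period.

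Three further points stand in part:
- The study is descriptive, and SAP 10.5 and section 13 openly plan both fixed and random models, so showing several estimates is not an error in itself.
- Protocol 9.7.4 gives no method for pooling IRRs, only for proportions and rates within each group. The contradiction with the protocol is therefore confined to the footnote.
- Country-level adjusted IRRs are reported regardless, and SAP Table 5 marks pooling as only a possibility for most outcomes.

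These limit the consequence. They do not make an odds test the right one for rate ratios.

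**Conclusion.** The plan is wrong as written in four specific places: Q and I-squared are defined on odds; three of seven estimators under an IRR title are binary-data methods; the input to the other four is unstated; and the Table 61 footnote misreports the protocol. Followed literally, the only heterogeneity statistic and three of the seven pooled values would not describe the adjusted IRR of objective 7.

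The numerical size depends on a quantity that the documents do not give. The odds-based results move roughly in proportion to the ratio of mean follow-up: a halving at 0.44 against 0.88 years, and almost no change at equal follow-up. The 66% against 0% for I-squared likewise rests on assumed follow-up ratios that differ between countries. Any distortion from dropping age and sex depends on how far the cohorts differ in those factors, which is also not given.

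**What to change.** In SAP 10.5, 16.4 and Tables 61–65:

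1. State that the inputs to all pooling are the three country-specific adjusted log IRRs and their log-scale standard errors from NOCDURNA_MAC7.
2. Pool them with mainverse (inverse variance) and marandom (random effects), and compute Q and I-squared from the same inputs. Remove the PROC FREQ odds test.
3. Drop the Mantel-Haenszel, logistic and normal-binomial rows, or relabel them as unadjusted odds ratios and keep them out of any table titled as an IRR.
4. Correct the Table 61 footnote to match protocol 9.7.4.
5. Preferably, name one method as the main estimate. This is advisable but secondary in a descriptive study.

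The cost is a change of SAP wording and shorter tables. The inputs are already planned in Table 29 and its repeats for the other pooled outcomes (Tables 32–36), and both macros are already listed in Table 69. No new data or country-level analyses are needed. The change should be made before the pooled analysis is programmed.
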